3.4 Efficacy Assessment

Efficacy data will be summarised by randomised/assigned treatment based on the mITT Population for the primary and on the ITT Population for the secondary endpoints. Sensitivity analysis will be performed on the ITT Population for the primary endpoint.

3.4.1 Primary Endpoint Analysis

Primary Analysis

The change in Hb concentration from baseline to Week 12 will also be summarised based on the mITT Population for each treatment group using descriptive statistics summarised by mean, standard deviation, median, and range (minimum and maximum).

The efficacy of ferric maltol will be assessed via the change in Hb concentration from baseline to Week 12 using a mixed model for repeated measures (MMRM) approach. The analysis will include fixed effects for treatment, visit, and treatment-by-visit interaction, along with a covariate of the baseline value as a continuous covariate. In the MMRM model, both assigned and randomised ferric maltol subjects will be included in the ferric maltol arm. A separate analysis will be performed only including randomised subjects.

If no interim analysis is conducted then 95% CIs will be displayed. If an interim analysis is conducted and the study does not stop after the interim analysis, the final analysis will be based on a (100-2.57)% two sided confidence interval.

The MMRM analysis will be implemented using SAS® Proc Mixed. Example SAS code can be found in Appendix C.

Sensitivity Analysis

Change in Hb concentration from baseline to Week 12, will be summarised for subjects randomised/assigned when the endpoint was designated as secondary and for subjects randomised/assigned after the endpoint was changed to a primary endpoint.

Change in Hb concentration from baseline to Week 12 will also be assessed for the ITT and PP population.

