- Post-treatment safety follow-up: 10-14 days following study completion of the treatment period or premature discontinuation

The randomisation scheme will be stratified by co-variates for age (2 yrs - 9 yrs, 10 yrs - 17 yrs) and sex (M/F). A minimum of 18 subjects must be recruited into each age group with 25% of either sex.

A maximum of 12 subjects will be recruited in the 1 months to < 2 years age group and they will only be assigned to ferric maltol. Once there is evidence of metabolism and elimination of maltol from Pre-assignment PK samples, they will continue to the Treatment Phase and be assigned to the ferric maltol arm. Subjects will be eligible to enter the treatment phase if their maltol level returns to baseline, or to a level confirming there is no accumulation of maltol or maltol glucuronide.

Where applicable country and local regulations and infrastructure for home healthcare allow, home healthcare may take place at a location other than the clinical trial site to perform study

CONFIDENTIAL Page 43 of 80

assessments, which may include but are not limited to collection of blood and urine samples, measurement of vital signs, length/height, and weight.

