9.2 RANDOMISATION (Visit 2)

Subjects will be registered into the study at the Screening visit and assigned a unique subject identification number in the IRT. Subjects will be categorised during the screening process based upon their age (2 to \leq 9 years of age and 10 to \leq 17 years of age) and their gender. Age and gender will be incorporated into the randomisation as stratification factors. A minimum of 18 subjects must be recruited into the 2-9 and 10-17 age group and a minimum of 25% of either sex must be recruited. Maximum of 12 subjects will be recruited in the 1 m - 2 yrs cohort. In the event of a subject having a birthday whilst on study and they move to a different age cohort -they will remain in the baseline cohort for the duration of the study.

A final eligibility evaluation must be conducted by the Investigator/designee prior to randomisation/pre-assignment PK visit via IRT, once the results of all Screening assessments are available.

Subjects aged 1 month to < 2 years:

Following the eligibility evaluation, a maximum of 12 subjects will enter a Pre-assignment phase: 1-day Pharmacokinetic assessment day following a single dose of 0.1 ml/kg ferric maltol oral suspension. Once the PK samples have been analysed and evidence is showing metabolism and elimination of maltol, subjects will be assigned to ferric maltol oral suspension treatment phase. Subjects will be eligible to enter the treatment phase if their maltol level returns to baseline, or to a level confirming there is no accumulation of maltol

CONFIDENTIAL Page 52 of 80

or maltol glucuronide. The sample results will be analysed on an individual basis. The Sponsor's Medical Monitor will make a recommendation to the investigator based on preassignment results. The investigator will make the final decision if subjects aged 1 month to < 2 years are eligible to enter the treatment phase.

Subjects aged 2 years to 17 years:

No subject may begin treatment prior to being randomised in the IRT. The randomisation procedure (created using a computer-generated random permutation procedure) will assign the subject to one of the treatment arms.

Initial dosing with ferric maltol and ferrous sulfate must occur on the same day of randomisation. The date of Visit 2 is the date of first dose with ferric maltol or ferrous sulfate.

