3.1.5 Hypothesis Testing

Hypothesis testing will be performed for the interim analysis to test the hypothesis that the ferric maltol Hb change from baseline to Week 12 is > 0. If an interim analysis is conducted, a Pocock spending function will be used; the interim analysis will be based on a (100-3.45)% two sided confidence interval.

The efficacy primary endpoint will also involve hypothesis testing. If no interim analysis is conducted the hypothesis testing will be based on a 95% two-sided confidence interval. If the study does not stop after the interim analysis, the final analysis will be based on a (100-2.57)% two sided confidence interval.

The study safety primary endpoints will be analysed by descriptive statistics only. The secondary endpoints will be analysed by descriptive statistics only. Thus, no formal testing strategy or adjustments of the Type I error will be employed for the evaluation of secondary endpoints.

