4 ANALYSIS TIMING

4.1 Interim Analysis

If less than 91 subjects in total have been randomised when 32 ferric maltol subjects have completed, then an interim analysis of the primary effectiveness endpoint (change in Hb concentration from baseline to Week 12) will be conducted. If significant, the study will stop recruitment. If not significant, the study will continue (all subjects will be assigned to ferric maltol) until 54 subjects have been recruited in the ferric maltol arm.

If an interim analysis is conducted, a Pocock spending function will be used. The interim analysis will be based on a (100-3.45)% two sided confidence interval. If the study does not stop after the interim analysis, the final analysis will be based on a (100-2.57)% two sided confidence interval.

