APPENDIX A: REFERENCES

APPENDIX B: LABORATORY TESTS

Clinical Chemistry

Albumin Alanine Aminotransferase

Alkaline Phosphatase Amylase

Aspartate Aminotransferase Blood Urea Nitrogen

Calcium Chloride
Creatinine Folate
Gamma-glutamyl Transferase Glucose

Phosphorous Potassium

Sodium Total Bilirubin

Total Cholesterol Total Protein
Uric Acid Vitamin B12

Hematology

Absolute reticulocyte count Haemoglobin

Haematocrit Mean Cell Volume

Statistical Analysis Plan Version 2.0 / 10-Jul-2024

Red blood cell count Platelet count White blood cell count (total and differential (% and absolute)) Iron Markers **Ferritin** Serum Iron Transferrin **Total Iron Binding Capacity** Transferrin Saturation **Unsaturated Iron Binding Capacity** APPENDIX C: SAMPLE CODE Note: USUBJID = Unique subject identifier TREATMENT = Treatment VISIT = Visit BASE = Baseline value CHG = Change from Baseline ****************************** proc mixed; class USUBJID TREATMENT VISIT;

model CHG=TREATMENT BASE VISIT TREATMENT*VISIT / solution cl;

repeated VISIT / type=UN sub=USUBJID;

Ismeans VISIT*TREATMENT/cl diffs;

run;

Note: In case the model will not converge with the unstructured covariance structure, the heterogeneous compound symmetry (CSH) or the heterogeneous Toeplitz structure (TOEPH) will be used instead.

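### The Hb model omits the stratification factors age group and sex: the formal ferric maltol test stands, but the comparison with ferrous sulfate may be less precise than it could be and has no named source

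*SAP*

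**What the plan says.** **Randomisation.** Protocol 7.1 says "The randomisation scheme will be stratified by co-variates for age" (2-9 and 10-17 years) and sex. Protocol 9.2 repeats it: "Age and gender will be incorporated into the randomisation as stratification factors". Protocol 8.6.1 agrees. Infants aged 1 month to under 2 years are not randomised; up to 12 are assigned to ferric maltol.

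**Model.** SAP 3.4.1: "The analysis will include fixed effects for treatment, visit, and treatment-by-visit interaction", plus continuous baseline Hb. The code in SAP Appendix C matches: "model CHG=TREATMENT BASE VISIT TREATMENT*VISIT / solution cl". Its LSMEANS line asks for `diffs`, so the between-arm difference at each visit is printed. Neither place has an age or sex term, and no reason is given.

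**Who is in the model.** SAP 3.4.1 says "both assigned and randomised ferric maltol subjects will be included in the ferric maltol arm". The next sentence plans a separate analysis restricted to randomised subjects.

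**What is tested.** SAP 3.1.5 sets the Hb test as one "to test the hypothesis that the ferric maltol Hb change from baseline to Week 12 is > 0". Without an interim, "the hypothesis testing will be based on a 95% two-sided confidence interval"; after an interim that does not stop the study, "the final analysis will be based on a (100-2.57)% two sided confidence interval". The Hb objective (SAP 2.1.1) covers 1 month to 17 years. No between-arm Hb hypothesis is stated in either document.

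**The concern.** A trial that balances its arms on two factors normally carries them into the model. If they predict the outcome and are left out, the between-arm estimate among randomised children stays unbiased. The model, however, does not credit the balance that stratification created, so its standard error is too large.

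The documents give reasons to expect some prognostic value beyond baseline Hb. The Hb entry limits in Protocol 7.3.1 run from 11.0 g/dl (under 5 years) to 13.0 g/dl (males from 13), so one baseline Hb can mean different deficits. The ferric maltol dose also changes with age (Protocol 5.5.2). How much variance the two factors explain is not stated.

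The pooling rule raises a second, separate issue. The printed difference compares an arm that contains infants with one that has none, so part of it may be an age difference. At stake is how a reader interprets a between-arm Hb figure in the study report, not the pass or fail of the efficacy endpoint.

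**Working it through.** **Inputs.** n = 49 per arm, SD of change 1.2 g/dL and mean change 0.5 g/dL (Protocol 12.1, SAP 2.2.4); two-sided 5% (SAP 3.1.5); at most 12 infants (SAP 2.2.2). Assumptions not in the documents: R², the share of Week 12 variance explained by age group and sex beyond baseline Hb (0 to 20%), and the difference in response between infants and older children (0 to 1.0 g/dL). The SD of 1.2 is used as the residual SD after baseline adjustment. The percentage narrowing does not depend on it.

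**1. The plan's own figure.** Within-arm power = Φ(0.5 × √49 / 1.2 − 1.96) = Φ(2.917 − 1.960) = 83.1%. With noncentral t on 48 df it is 81.5%. The stated figure of at least 80% is reproduced. For a between-arm difference of 0.5 g/dL the same inputs give SE = 1.2 × √(2/49) = 0.242 and power Φ(0.5/0.2424 − 1.96) = 54%. The trial is not sized for that contrast.

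**2. Precision of the contrast, randomised children only.** SE = 1.2 × √(1 − R²) × √(1/49 + 1/49); half-width = 1.96 × SE.

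| Assumed R² | SE (g/dL) | 95% half-width (g/dL) | CI narrower by, 1 − √(1 − R²) |
|---|---|---|---|
| 0 | 0.242 | 0.475 | 0% |
| 5% | 0.236 | 0.463 | 2.5% |
| 10% | 0.230 | 0.451 | 5.1% |
| 20% | 0.217 | 0.425 | 10.6% |

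**3. Simulation of the same contrast.** There were 6,000 trials per scenario with 98 children, blocks of four within age-by-sex cells, no true treatment difference and no missing data. Each trial was analysed by ANCOVA of Week 12 change on baseline, which is simpler than the MMRM. Bias was about zero throughout.

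| R² | True sampling SD, factors omitted | Mean model SE, factors omitted | Type I error, omitted | Type I error, included |
|---|---|---|---|---|
| 0 | 0.244 | 0.243 | 4.8% | 4.9% |
| 10% | 0.234 | 0.243 | 4.1% | 5.1% |
| 20% | 0.219 | 0.243 | 3.0% | 5.0% |

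Monte Carlo error near 5% is √(0.05 × 0.95 / 6000) = 0.3 points. The omission makes the contrast conservative, not wrong.

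**4. Infants in the pooled model.** At full recruitment the infant share of the ferric maltol arm is 12/(49 + 12) = 12/61 = 0.197. Shift in the contrast = 0.197 × infant difference. The unadjusted SE is 1.2 × √(1/61 + 1/49) = 0.230.

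| Assumed infant difference (g/dL) | Shift (g/dL) | Shift in SEs | Type I error, plan's terms (R² 10%) | With age, sex and an infant level |
|---|---|---|---|---|
| 0 | 0 | 0 | 4.0% | 5.0% |
| 0.5 | 0.098 | 0.43 | 5.3% | 4.4% |
| 1.0 | 0.197 | 0.85 | 10.7% | 5.4% |

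An infant level removes the shift. The two-level age factor used for stratification would not, because it has no infant category.

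**5. Weighting.** If a three-level age group is added to the pooled model, default LS means weight the levels equally. Infants would then count for 1/3 of the ferric maltol mean, against at most 19.7% of the arm.

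**The case against.** The strongest reply is that the contrast is not what the plan tests. The Hb hypothesis, the power statement and the interim rule all concern the change within the ferric maltol arm. The contrast arises only from an option in example code. That stands, and it rules out two stronger readings that a reader might infer.

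- *That the primary efficacy test is biased or loses its stated power.* The documents do not support this. The test is within-arm, and its power reproduces without any between-arm comparison. An argument remains that the missing-at-random assumption would be more plausible given age and sex, but nothing in the documents allows it to be sized.
- *That infants contaminate the primary result.* For the tested quantity, including them matches the stated objective of 1 month to 17 years. The mixing affects only the difference from ferrous sulfate. It comes from the pooling rule, not from the missing factors.

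A second reply is that the planned randomised-only analysis already removes every infant, and also any older child assigned to ferric maltol after a non-significant interim. This stands too. What it leaves open is that no strata terms are named for that analysis, and the SAP does not say that the contrast is to be read from it.

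A third reply is that the gain may be negligible, because baseline Hb may already carry most of the age and sex effect. This cannot be excluded. Likewise, 12 infants is a ceiling: Protocol 12.1 allows the study to finish without that cohort.

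**Conclusion.** The point holds in a limited form, as a minor, nearly free improvement. Both stratification factors are missing from the Hb model in text and code, without a stated reason. The formal within-arm ferric maltol test is neither biased nor invalidated by this.

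For the ferric maltol versus ferrous sulfate difference there are two consequences:

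- The confidence interval is wider than needed if age and sex are prognostic beyond baseline Hb: by adding them it would narrow by about 0 to 11% for an assumed R² of 0 to 20%. The true figure is unknown.
- In the pooled model, the difference moves by up to 0.10 g/dL for each assumed 0.5 g/dL difference in infant response, at the planned 49 + 12 subjects.

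The remaining gap is that the SAP does not say which of its two analyses supplies this contrast, or that the contrast is descriptive.

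**What to change.** 1. **Randomised-only MMRM (SAP 3.4.1 and Appendix C).** Add age group (2-9, 10-17) and sex to the class and model statements, each with its interaction with visit. State that any ferric maltol versus ferrous sulfate Hb contrast is descriptive and is read from this model.
2. **Pooled MMRM, if it is adjusted as well.** Use a three-level age group (1 month to <2, 2-9, 10-17 years) plus sex. Report the ferric maltol LS mean at that arm's observed age and sex mix, and write out the LSMEANS code with those weights so that infants do not receive one-third weight by default. Infants have no scheduled Day 28 haematology, so an age-by-visit term here would have an empty infant cell at that visit.

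**Cost.** With scheduled post-baseline Hb at Days 28 and 84, step 1 adds four parameters (two main effects, two visit interactions). Step 2 adds three as main effects. The code is slightly longer. Both factors are already collected, so no new data are needed.

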3.4.2 Secondary Endpoints Analysis

The secondary endpoints will be reported for each treatment group using descriptive statistics summarised by mean, median, and range (minimum and maximum), and 95% confidence interval for the mean where applicable, split by age group.

Any measurement obtained after a patient received a blood transfusion, or received an intravenous iron or erythropoiesis stimulating agent (ESA) will be excluded from the analysis.

The secondary endpoints are as follows: PK analysis of Serum Iron, Corrected serum iron, TSAT, Transferrin, TIBC, UIBC, Maltol and Maltol Glucuronide.

Descriptive summary statistics will be summarised for children and adolescents aged 1 month to 17 years in the ferric maltol group for the PK analysis of Serum Iron, Corrected serum iron, TSAT, Transferrin, TIBC, UIBC, Maltol and Maltol Glucuronide.

Changes in iron markers from baseline to Weeks 4 and 12

The secondary analysis of the change from baseline to Weeks 4 and 12 in iron markers (serum iron, serum corrected iron, transferrin, TSAT, TIBC, UIBC and ferritin) will be summarised using descriptive summary statistics. In this analysis, missing Week 12 and Week 4 values will be imputed using a LOCF (last observation carried forward) approach in which the last available post-baseline measurement will be used in the analysis.

Achieving Hb concentration within normal range at Week 12

The number and percentage of subjects achieving normal range, based on the central laboratory's normal reference range, at Week 12 will be summarised by treatment group.

Qualitative assessments from subject questionnaires that allow evaluation of the acceptability, palatability and ease of use

Qualitative assessments from subject questionnaires that evaluate acceptability, palatability and ease of use will be summarised separately for children aged 5 and under and those aged 6 and over.

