7.4 CONCOMITANT MEDICATION

7.4.1 Not Permitted

- Treatment with single agent oral iron preparation (prescription and non-prescription) within 7 days prior to screening and throughout the study period.
- Treatment with parenteral iron preparations within 28 days prior to screening and throughout the study period.
- Blood transfusions within 12 weeks before screening and during the study.
- Erythropoiesis stimulating agents within 28 days before screening and during the study.

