7.5 INDIVIDUAL DISCONTINUATION CRITERIA

Subjects and/or their parents or guardians have the right to withdraw consent without prejudice at any time during the study. If a subject withdraws consent, the Investigator should make a reasonable effort to determine the cause. All withdrawn subjects should have a Post-Treatment Safety Visit within 10-14 days after the last dose of study drug (if the subject agrees in the case of withdrawn consent).

If there is any sign of accumulation of maltol or glucuronide in the pre-assignment phase PK day for subject population aged 1 month to less than 2 years, the recruitment to this age group will be suspended and they will not enter the treatment phase until the risk has been assessed and approved via a substantial amendment to the protocol.

Subjects may be discontinued prematurely during the study for the following reasons:

- Withdrawal of informed consent
- A drop of >1 g/dl in Hb from baseline
- Unwillingness or inability to comply with protocol requirements
- Pregnancy or not using a reliable method of birth control (female subject of childbearing potential)
- Use of prohibited concomitant medications
- Serious adverse events that are judged by the Investigator to be related to study treatment

CONFIDENTIAL Page 47 of 80

- Blood transfusions for any cause during the study treatment period
- Use of any other single agent prescribed iron medications
- Occurrence of any condition that, in the opinion of the Investigator, significantly
 jeopardizes the wellbeing and safety of the patient, including any intolerable toxicity
 related to study treatment determined by the investigator to be unacceptable given
 the severity of the event

The reason for study drug discontinuation and the date of last dose should be recorded in the eCRF. Subjects who discontinue treatment prematurely must return for the Post-Treatment Safety Visit, unless informed consent is withdrawn (and the subject and/or their parents or guardians do not agree to attend this follow-up visit). A subject who meets discontinuation criteria should be discussed on an individual basis with the Medical Monitor.

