3.1.2 Analysis Visits

Scheduled visits will be assigned to analysis visits as recorded on the case report form (CRF). The record occurring on the target day will be picked for analysis. If the record on a target day does not exist, then the one closest to the target date will be used. Unscheduled and early termination visits will be assigned to analysis visits according to the following visit windows:

Analysis Visit	Target Analysis Day	Low Analysis Day	High Analysis Day
Day 1	1	NA	NA
Day 7-10	7	2	17
Day 28	28	18	42
Day 56	56	43	70
Day 84	84	71	No upper limit

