3.6.2 Clinical Laboratory Tests

Clinical Chemistry and Haematology will be collected at the Screening Visit and Visit 6 (Day 84). In addition, Haematology will be collected at Visit 4 (Day 28) for those subjects in the 2-17 years of age group. Additionally, Hematology and iron markers will be collected at Visit 2 for the 1 month to < 2 years age group.

At Visit 7, Clinical Chemistry and Haematology will be collected if the subject has an ongoing AE that requires onsite assessment/management, or if the subject early discontinued.

Chemistry parameters include vitamin B12, folate, alanine aminotransferase (ALT), aspartate aminotransferase (AST), alkaline phosphatase (ALP), gamma-glutamyl transpeptidase (GGT), total bilirubin, creatinine, amylase, blood urea nitrogen (BUN), phosphorous, sodium, potassium, chloride, calcium, total cholesterol, uric acid, glucose, total protein, albumin.

Haematology parameters include red blood cell count, haemoglobin, haematocrit, mean cell volume (MCV), white blood cell count (total and differential (% and absolute)), absolute reticulocyte count and platelet count.

Descriptive statistics for each safety laboratory parameter will be presented for baseline values and for values and the change from baseline at each post-baseline visit.

Values outside the normal range will be categorised as below the lower limit of normal or above the upper limit of normal based on the central laboratory's normal reference range. Values

outside of the normal range will be summarised. Shifts from baseline to worst post-baseline category will be tabulated by laboratory parameter and shift category (low to low, normal to low, high to low, low to normal, normal to normal, high to normal, low to high, normal to high or high to high) for chemistry and haematology parameters.

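### Hb values after transfusion, IV iron or ESA are dropped from the secondary endpoints but, by default, kept in the primary Hb test and the interim stopping test

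*SAP*

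**What the plan says.** **Secondary endpoints.** SAP 3.4.2 states: "Any measurement obtained after a patient received a blood transfusion, or received an intravenous iron or erythropoiesis stimulating agent (ESA) will be excluded". The endpoint of Hb within the normal range at Week 12 falls under that heading.

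**Primary Hb endpoint.** SAP 3.4.1 fits an MMRM to the change in Hb, and "both assigned and randomised ferric maltol subjects will be included in the ferric maltol arm". SAP 3.1.5 describes the interim test as one to "test the hypothesis that the ferric maltol Hb change from baseline to Week 12 is > 0" and bases the final efficacy test on a confidence interval for the same endpoint. For the interim, SAP 4.1 adds: "If significant, the study will stop recruitment". None of these sections, nor the sample code in Appendix C, mentions transfusion, IV iron or ESA.

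**Defaults.** SAP 3.1.6 uses observed data without imputation unless otherwise specified. Protocol 12.2.4 uses all data as available. SAP section 5, which lists departures from the protocol, does not mention the exclusion.

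**Conduct.** Protocol 7.4.1 lists as not permitted "Blood transfusions within 12 weeks before screening and during the study", and also parenteral iron and ESAs. The discontinuation list in protocol 7.5, which includes transfusion, opens permissively: "Subjects may be discontinued prematurely during the study for the following reasons". SAP 3.1.2 says: "Unscheduled and early termination visits will be assigned to analysis visits according to the following visit windows"; the Day 84 window starts at day 71 and has no upper limit.

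**The concern.** The sponsor has judged Hb values after these treatments unfit for descriptive endpoints, but the one formal test has no matching rule. That test asks whether the mean change within the ferric maltol arm exceeds zero. Ferrous sulfate data sit in the model but are not subtracted, so any Hb gain from a transfusion or IV iron moves the result toward success and nothing offsets it. At the interim the same result decides whether recruitment stops. Because the trial is open-label, a choice made after data have been seen would be a data-driven decision on a primary endpoint.

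**Working it through.** **1. What happens to one affected Week 12 Hb**

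| Analysis | Governing text | Value is |
|---|---|---|
| Hb within normal range | SAP 3.4.2 exclusion | dropped |
| Primary Hb MMRM | SAP 3.4.1 silent; defaults in SAP 3.1.6 and protocol 12.2.4 | kept |
| Interim test | SAP 3.1.5 and 4.1 silent; same defaults | kept |
| Per-protocol sensitivity analysis | SAP 3.2.2 and 3.4.1; major deviation not defined | possibly dropped |

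**2. Can such a value arise?** Yes, by two routes. A treated child may stay on study to Week 12, since discontinuation is optional. Or an unscheduled or early-termination result may fall on day 71 or later. SAP 3.6.2 provides for haematology at Visit 7 after early discontinuation, and Visit 7 comes 10-14 days after the last dose. This second route is narrow: the last dose must be on about day 57 or later (57 + 14 = 71).

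**3. The plan's own power figure.** Inputs (protocol 12.1, SAP 2.2.4): n=49, mean change 0.5, SD 1.2, 95% two-sided interval. One-sample noncentral t with noncentrality 0.5 x sqrt(49)/1.2 = 2.92 and critical value 2.01 gives 81.5%, consistent with the stated minimum of 80%.

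**4. Size if values are kept (illustration).** The documents give neither a rate nor an Hb gain. Assumed: k = 1 to 3 children, +2 g/dL each, true change 0, SD 1.2. The mean shifts by 2k/n; at n=32 that is 2/32 = 0.06 to 6/32 = 0.19 g/dL. The mean needed for significance there is 2.21 x 1.2/sqrt(32) = 0.47 g/dL. False success is the simulated chance that the lower bound exceeds zero, using a one-sample t test as a stand-in for the MMRM:

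| Look | Two-sided alpha | k=0 | Random children, kept, k=1 to 3 |
|---|---|---|---|
| Interim, n=32 | 3.45% | 1.7% | 2.8-6.8% |
| Final without interim, n=49 | 5% | 2.5% | 3.7-8.0% |
| Final after interim, n=54 | 2.57% | 1.3% | 1.9-4.3% |
| Final without interim, 49 + 12 infants = 61 | 5% | 2.5% | 3.6-7.3% |

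**5. Does exclusion alone cure it?** Not if the children treated are those with the lowest Week 12 change:

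| n | Kept | Excluded |
|---|---|---|
| 32 | 4.6-18.2% | 4.8-16.9% |
| 49 | 5.2-15.5% | 5.8-16.8% |
| 61 | 4.8-13.0% | 5.4-15.1% |

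The next table adds a Day 28 Hb to the model at n=32 (assumed correlation with Week 12 of 0.3 to 0.7; k = 1 and 3):

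| Who is treated | Kept | Excluded | Day 28 value carried to Week 12 |
|---|---|---|---|
| Lowest at Day 28 | 3.2-13.2% | 1.6-1.9% | 0.1-1.1% |
| Lowest at Week 12 | 4.5-18.1% | 3.3-14.8% | 2.6-9.6% |

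In both cases the pre-treatment value gives the lowest rate.

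**6. Who has a pre-treatment value?** SAP 3.6.2 says: "Haematology will be collected at Visit 4 (Day 28) for those subjects in the 2-17 years of age group". Infants under 2 years have no scheduled Hb between Visit 2 and Day 84, so most would have no post-baseline value to carry.

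**The case against.** - **A default exists.** A reader might infer that the plan has no rule at all for these values in the primary analysis. The documents do not support that: SAP 3.1.6 and protocol 12.2.4 settle the matter in favour of keeping them. What stands is that the default conflicts with SAP 3.4.2 and the difference is not justified. A generous reader could take the sentence in 3.4.2 as general, but its heading and position do not support that.
- **Cases should be rare.** The treatments are prohibited. Protocol 7.3.2 also excludes children with scheduled transfusion, extensive active bleeding, eGFR below 60, or expected hospitalisation or surgery. This stands, and it limits the likely size.
- **The error rates assume no drug effect.** This is fair. At a true change of 1 g/dL, interim power is about 99% with 32 or 29 subjects, so the decision would barely move.
- **The per-protocol analysis may remove these children.** It may, and deviations are reviewed before database lock. But a major deviation is not defined, and no per-protocol analysis is stated for the interim.
- **Exclusion is not clearly better than keeping the values.** This is correct when the lowest Week 12 responders are treated, as step 5 shows. It argues for a companion analysis, not for leaving the two rules in conflict.

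**Conclusion.** The inconsistency is certain from the text. As written, a gain from a prohibited blood or iron treatment is credited to ferric maltol in the only hypothesis test and removed from a descriptive endpoint built on the same Hb. Any such gain pushes toward success.

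The size is unknown and probably small; with no affected child there is no effect. A reader might take the figures above, especially the 18%, as the trial's actual false-success rate. They are not. They rest on an assumed number of children, an assumed +2 g/dL, a true change of zero and a t test in place of the MMRM; the largest also assume that the poorest responders are the ones treated. A reader might also infer that exclusion alone removes the bias; step 5 shows that it need not. No figure stated in the plan is wrong on this point.

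Severity is low to moderate: a cheap improvement, best settled before the data are seen.

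**What to change.** 1. **One rule.** Move the existing exclusion sentence to the head of SAP 3.4 so that it covers the primary Hb analysis, at interim and final, and the secondary endpoints. Record it in SAP section 5.
2. **A companion sensitivity analysis at each look.** Exclusion treats affected children as missing at random. Add an analysis that takes each affected child's last Hb before the treatment, unscheduled values included, as the Week 12 value. Record it in section 5 as a departure from protocol 12.2.4.
3. **Children with no post-baseline Hb before the treatment**, mainly infants. Do not default to zero change. Show the result over a range of unfavourable assumed changes, with the values chosen by the sponsor in advance.

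**Cost.** SAP wording, the section 5 entries and one extra analysis per look. The estimate may move either way. Power at a mean change of 0.5 and SD 1.2, counting each of three exclusions as a whole lost subject:

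| Look | All subjects | Three excluded |
|---|---|---|
| Interim, n=32, 3.45% | 56.3% | 51.6% |
| Final, n=49, 5% | 81.5% | 79.0% |
| Final after interim, n=54, 2.57% | 77.6% | 74.9% |
| Final with infants, n=61, 5% | 89.3% | 87.7% |

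The loss is smaller where the MMRM retains a Day 28 value.
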